#### Analysis of Secondary Efficacy Endpoints:

Analysis of binary secondary efficacy endpoints (hemoglobin response on at least one visit, achievement of a change from Baseline in hemoglobin level of 2 g/dL or greater, use of permitted rescue medications after Week 4) will be performed using the CMH test stratified by concomitant steroid use at Baseline ( $\geq 20$  vs.  $< 20$  mg daily), and Screening hemoglobin level  $< 9$  vs.  $\geq 9$  g/dL). In addition, the exact Clopper-Pearson 95% CI for the overall proportions will be estimated by treatment group. In addition, the Agresti-Min exact unconditional 95% CI for the difference in proportions will be estimated as well as the 95% Miettinen-Nurminen score CIs taking into account the stratification factors.

Change from Baseline to End of Treatment in hemoglobin levels will be analyzed using an analysis of variance (ANOVA) model with multiple imputations with concomitant steroid use at Baseline ( $\geq 20$  vs.  $< 20$  mg daily), screening hemoglobin level ( $< 9$  vs.  $\geq 9$  g/dL) and treatment group as fixed effect in the model. The missing hemoglobin values will be imputed. Least squares mean with the 95% CI for the mean will be constructed for each treatment group and for the differences between the treatment groups.

Change from Baseline to Week 12 and Week 24 in the FACIT-F will be analyzed using Mixed effect model for repeated measures implemented by SAS PROC MIXED. The model will use change from Baseline in FACIT-F as a response variable and include the fixed categorical effects of treatment group, weeks (12 and 24), interaction between treatment and weeks, concomitant steroid use at Baseline ( $\geq 20$  vs.  $< 20$  mg daily), Screening hemoglobin level ( $< 9$  vs.  $\geq 9$  g/dL), and Baseline FACIT-F as a covariate.

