#### 4.3 Secondary Efficacy Endpoints

The secondary efficacy endpoints within the 24 weeks of treatment are:

1. Hemoglobin response on at least one visit (Yes/No)
2. Achievement of a change from Baseline in hemoglobin level of 2 g/dL or greater (Yes/No)
3. Change in hemoglobin value from Baseline to End of Treatment (Week 14 to Week 24)
4. Use of permitted rescue medications after Week 4 (Yes/No)
5. Change from Baseline to Week 24 in Functional Assessment of Chronic Illness Therapy - Fatigue scale (FACIT-F)

End of Treatment hemoglobin is defined as the mean of the hemoglobin values from the last 6 available visits between Week 14 and Week 24, inclusive, as long as those visits occurred outside a Rescue Treatment Visit Exclusion Period.

The FACIT-F scale is a short, 13-item, easy to administer tool that measures an individual's level of fatigue during their usual daily activities over the past week. Each item is rated using a 5-point Likert-type scale (0 = not at all; 1 = a little bit; 2 = somewhat; 3 = quite a bit; and 4 = very much). Negatively stated items are reversed by subtracting the response from "4". After reversing proper items, all subscale items are summed to a total, which is the subscale score. All items contribute to the sum score with equal weight. The scale range is 0 to 52, with 0 being the worst possible score and 52 being the best possible score indicating no fatigue (see FACIT

Administration and Scoring Guidelines, and Cella 2002). The overall score will be calculated and prorated for missing items as follows:

$$\text{Total Score} = [\text{Sum of item scores}] \times [\text{N of items in subscale}] \div [\text{N of items answered}]$$

The FACIT-F change scores will be computed as (Week 24 score - Baseline score).

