## 7.9 Rescue Protocol

Use of rescue medications including increases in steroid doses should be avoided for the duration of the study unless medically necessary. Rescue may be given following a decrease in Hgb of  $>1.5$  g/dL from baseline **OR** new or worsening symptoms of anemia, so long as urgent treatment is required in the judgment of the Investigator. In subjects meeting these criteria, the following rescue regimens are permitted:

1. Increase or initiate steroid dose up to 80 mg/daily prednisone (or equivalent) for approximately 2 weeks or until clinically stable, then taper the dose by 10 to 20 mg prednisone (or equivalent) per week until return to baseline dose level (see [Appendix 3](#) for prednisone equivalents conversion table);
2. IV methylprednisolone up to 1 g/day x 1 day up to 3 days;
3. Oral dexamethasone up to 40 mg/day x up to 4 days;
4. Red blood cell (RBC) transfusion;
5. IVIg: up to 1g/kg x 1 day up to 3 days.

The Investigator must discuss all instances of rescue therapy with the Sponsor's Medical Monitor in advance of initiating the therapy whenever possible. The use of any rescue therapy regimen not noted above is not permitted. Only the rescue regimens above are allowed.

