#### **10.3.2 Enrollment Exceptions and Protocol Deviations**

Major protocol deviations related to study inclusion or exclusion criteria, conduct of the trial, subject management or subject assessment will be listed by site. Major protocol deviations are deviations that may significantly affect the completeness, accuracy, and/or the reliability of the study data or that might significantly affect a subject's rights, safety and well-being. Examples of major protocol deviations are:

- Subject enrolled who does not meet eligibility criteria
- Subject who used non-permitted rescue medications
- Improper collection of or failure to collect the initial study informed consent
- Subject who received treatment that was contrary to their randomization assignment
- Subject who developed withdrawal criteria during the study but was not withdrawn.

Protocol deviations will be maintained in the trial master file and will be listed and discussed in the clinical study report.

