### **10.3.6 Analysis of Primary Efficacy Endpoint**

The primary efficacy endpoint is achievement of durable hemoglobin response (Yes/No) defined as achieving a hemoglobin level  $\geq 10$  g/dL with an increase from Baseline in hemoglobin level of  $\geq 2$  g/dL on 3 consecutive available visits during the 24-week treatment period, in which hemoglobin measurements eligible for this definition occurred outside a Rescue Treatment Visit Exclusion Period.

Available visits are defined as any scheduled visit where a plasma sample was collected, and hemoglobin level analyzed using either central or local laboratory.

For permitted rescue medications, a Rescue Treatment Visit Exclusion Period begins with the initiation of the rescue medication. The end of a Rescue Treatment Visit Exclusion Period is 4 weeks (28 days) following the return of steroid use to Baseline level or the last administration of rescue medication, whichever event occurs the latest. Any hemoglobin measurements made during this exclusion period are not eligible for any endpoint definition.

For non-permitted rescue medications, a Rescue Treatment Visit Exclusion Period begins with the initiation of the rescue medication and ends at Week 24/Week 26 or date of early termination from study.

If durable hemoglobin response cannot be determined because the subject discontinued from the study prior to attaining a durable response, then the subject will be assumed as not having achieved a durable response.

Analysis will be performed after all randomized subjects have completed the 24 weeks of treatment or discontinued from the study. All subjects randomized will be included in the analysis (ITT population). The following hypothesis will be evaluated:

$$H_0: \Theta_{\text{Fostamatinib,Placebo}} = 1$$

$$H_a: \Theta_{\text{Fostamatinib,Placebo}} \neq 1,$$

where  $\Theta_{\text{Fostamatinib,Placebo}}$  is the odds ratio of durable hemoglobin response due to treatment.

Analysis will be performed using Cochran-Mantel-Haenszel (CMH) test stratified by concomitant steroid use at Baseline ( $\geq 20$  vs.  $< 20$  mg daily), and screening hemoglobin level ( $< 9$  vs.  $\geq 9$  g/dL). The odds ratio will be presented along with the 95% CI. The study will be considered to meet its primary efficacy objective if the lower bound of the 95% CI of the odds ratio of durable hemoglobin response between the Fostamatinib and Placebo-treated subjects is greater than 1.

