### 10.3.7 Analysis of Secondary Efficacy Endpoints

The secondary endpoints for this study are: hemoglobin response on at least one visit (Yes/No), achievement of change from Baseline in hemoglobin level  $\geq 2$  g/dL (Yes/No), change in hemoglobin values from Baseline to End of Treatment (Week 14 to Week 24), the use of permitted rescue medications after Week 4 (Yes/No), and change from Baseline to Week 24 in Functional Assessment of Chronic Illness Therapy - Fatigue scale (FACIT-F).

Adjustment for multiple testing using the hierarchical method as described in [Section 10.4](#).

The proportion of subjects who achieve hemoglobin response on at least one visit, proportion of subjects who achieve a change from Baseline in hemoglobin level  $\geq 2$  g/dL, and proportion of subjects using permitted rescue medications after Week 4 will be summarized. All subjects randomized will be included in the analysis (ITT population). Subjects with no assessment for hemoglobin response will be treated as non-responders. Subjects with no assessment for change from Baseline in hemoglobin level will be treated as failure to achieve a change from Baseline in hemoglobin level  $\geq 2$  g/dL.

Analysis of hemoglobin response on at least one visit, change from baseline in hemoglobin level  $\geq 2$  g/dL, and use of rescue medications after Week 4 will be performed using the CMH test stratified by concomitant steroid use at Baseline ( $\geq 20$  vs.  $< 20$  mg daily), and Screening hemoglobin level  $< 9$  vs.  $\geq 9$  g/dL). In addition, the exact Clopper-Pearson 95% CI for the overall proportions will be estimated by treatment group. In addition, the Agresti-Min exact unconditional 95% CI for the difference in proportions will be estimated as well as the 95% Miettinen-Nurminen score CIs  taking into account the stratification factors.

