### **On Study Visits:**

If possible, study patients should continue on study without interruption of the dosing and visit schedule.

If in-clinic visits are not possible, consideration can be given to continuing a subject on study drug without clinic visits as outlined below:

- Subjects should continue on study medication based on their safety and efficacy response to date (including an evaluation of all labs including ALT, AST, total and direct bilirubin (i.e., fractionated bilirubin), WBC, hemoglobin, hematocrit, and ANC; and any adverse events) up to 6-8 weeks without an in-person clinic visit. This is to be managed on a patient per patient basis at the discretion of the Investigator and in collaboration with the Medical Monitor.
- Subjects should have labs and blood pressure checked by their local physician/laboratory. Alternatives may include an at-home visit conducted by a study nurse. As a last resort, blood pressure may be checked with a home monitoring system and the site should contact subjects every 2 weeks to check for compliance and adverse events and any other information regarding their general status. Results should be shared with the Investigator for treatment decisions and documented in the medical record.
- If necessary, subjects may interrupt study drug and receive rescue treatment as needed for the underlying disease until restart of study drug, once in-clinic visits are resumed. Subjects are encouraged to stay on the study. The Investigator can consider this as a dose interruption. If an Investigator has concerns about a prolonged interruption, he/she should contact the Medical Monitor.
- Subjects reaching Week 24 visit who are unable to attend an in-clinic visit, should be discussed with the Medical Monitor.

Each patient has individualized needs and may miss an unknown number of visits, in the event of questions the Medical Monitor should be contacted.

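### Secondary endpoint 4 counts only permitted rescue, so a subject whose only AIHA rescue after Week 4 is non-permitted is scored as rescue-free

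*Combined protocol and SAP*

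**What the plan says.** - **Definition.** Section 4.3 lists the fourth secondary endpoint as "Use of permitted rescue medications after Week 4 (Yes/No"). The objective in section 4.1, the synopsis and the endpoint list in section 10.3.7 carry the same restriction.
- **What is permitted.** Section 7.9 lists five regimens: oral steroid increase or initiation, IV methylprednisolone, oral dexamethasone, RBC transfusion and IVIg. It then closes the list: "The use of any rescue therapy regimen not noted above is not permitted".
- **Non-permitted rescue elsewhere.** Section 10.3.2 gives "Subject who used non-permitted rescue medications" as an example of a major deviation. Section 10.3.6 says "For non-permitted rescue medications, a Rescue Treatment Visit Exclusion Period begins with the initiation of the rescue medication and ends at Week 24/Week 26", or at early termination. After permitted rescue the exclusion lasts 28 days from the later of the last rescue dose and the return of steroids to their Baseline level.
- **Withdrawal.** The synopsis and section 7.14.1 say that subjects who need other AIHA therapy, or escalation of an allowed non-steroid therapy, should be withdrawn. Section 7.6 lists the same need among the reasons for which a subject may be withdrawn.
- **Analysis.** Section 10.3.7 analyses the binary secondary endpoints in all randomized subjects. It sets an unfavourable-outcome rule for missing assessments on endpoints 1 and 2, and none for endpoint 4. Its summary sentence reads "proportion of subjects using permitted rescue medications after Week 4 will be summarized". Its test sentence reads "and use of rescue medications after Week 4 will be performed using the CMH test", without the word permitted. The synopsis keeps the word: "use of permitted rescue medications after Week 4) will be performed using the CMH test".
- **Testing order.** Section 10.4 tests the five secondary endpoints in sequence at 0.05 after the primary, so endpoint 4 comes fourth and FACIT-F last.

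**The concern.** A rescue endpoint is read as a measure of who needed extra treatment for the disease. Under the stated definition, a subject who goes straight to an unlisted therapy is counted with those who needed nothing. This is the reverse of the rest of the plan, where non-permitted rescue carries the heavier consequence. Endpoint 4 is in the alpha-controlled sequence, so its result can support a formal claim and also decides whether FACIT-F is tested. If the misplaced subjects are on placebo, a real difference is partly masked. If they are on fostamatinib, the drug looks better than it was.

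**Working it through.** **Who is affected**

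| Rescue after Week 4 | Endpoint 4 as written | Any-rescue definition |
|---|---|---|
| None | No | No |
| Permitted only | Yes | Yes |
| Permitted and non-permitted | Yes | Yes |
| Non-permitted only | **No** | **Yes** |

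Only the last row changes. Withdrawal does not remove these subjects, because the analysis set is ITT. An observed non-permitted rescue is also not a missing value, so a missing-data rule need not reach it.

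**Size: inputs**

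The plan states no figure for endpoint 4, so there is none to reproduce. From the documents: 45 subjects per arm (section 10.1) and a significance level of 0.05 (section 10.4), taken as two-sided. The documents give no rescue rates, so every rate below is assumed. Each subject is worth 1/45 = 2.2 percentage points in an arm.

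The test is the CMH statistic without continuity correction, simplified to one stratum. With a and b subjects scored Yes on fostamatinib and placebo, and m = a + b:

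X² = (a − m/2)² / V, where V = 45 × 45 × m × (90 − m) / (90² × 89), on 1 degree of freedom.

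**Hiding placebo subjects.** Start from a true 9 vs 20. Then m = 29, V = 4.969, X² = 5.5²/4.969 = 6.088 and p = 0.014.

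| Placebo subjects scored No in error | Counts analysed | p |
|---|---|---|
| 0 | 9 vs 20 | 0.014 |
| 1 | 9 vs 19 | 0.024 |
| 2 | 9 vs 18 | 0.040 |
| 3 | 9 vs 17 | 0.064 |

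**Hiding fostamatinib subjects.** Suppose the literal count is 10 vs 20 (p = 0.026). If one fostamatinib subject was hidden, the true count is 11 vs 20 (p = 0.047). If two were hidden, it is 12 vs 20 (p = 0.080).

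**How often the verdict changes.** These come from exact enumeration of both binomial distributions:

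| Assumed true need, fostamatinib / placebo | Significance lost: 1 / 2 placebo subjects hidden | Significance gained: 1 / 2 fostamatinib subjects hidden |
|---|---|---|
| 10% / 30% | 8.6% / 17.8% | 11.0% / 19.2% |
| 20% / 40% | 8.7% / 17.2% | 10.0% / 19.1% |
| 20% / 45% | 7.6% / 15.8% | 7.7% / 14.0% |
| 20% / 50% | 5.2% / 11.5% | 4.9% / 8.4% |
| 30% / 50% | 8.1% / 15.7% | 9.3% / 18.3% |

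**Power.** At 20% vs 45% it is 72.7%. If 5% of need is hidden in both arms, the rates become 0.95 × 20% = 19% and 0.95 × 45% = 42.75%, and power is 69.3%. If it is hidden in placebo only (20% vs 42.75%), power is 65.0%.

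All these figures are unconditional. In the trial, endpoint 4 is tested only after the primary and secondaries 1 to 3 have succeeded.

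**The case against.** The strongest reply is that the endpoint matches its objective: both say permitted rescue, and the plan never promises a measure of all rescue need. That is true, and widening the endpoint does change the question. But it does not explain why the event treated most severely elsewhere should earn the favourable score here.

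A second reply is that these subjects should leave the trial, and that section 10.6 defers dropout handling to the SAP. This stands in part. The group is meant to be small, and the SAP may score some withdrawals. It does not settle the scoring, for the ITT and observed-event reasons above.

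Third, the permitted list is broad. A subject must use none of the five regimens after Week 4 and still receive something else. This stands, and it is why the number is probably small. Such subjects also lose hemoglobin eligibility, which bears on the primary and on secondaries 1 to 3. Time to first rescue medication (section 4.5) is not limited to permitted rescue, but section 10.3.8 makes it supportive, without multiplicity control.

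Fourth, the arithmetic shows fragility, not bias: moving one or two subjects alters any comparison of this size near 0.05. That stands too.

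Three stronger readings are tempting, and the documents do not support them:
- **Appendix 7 as a second route.** It says "subjects may interrupt study drug and receive rescue treatment as needed for the underlying disease until restart of study drug", and a reader might infer that unlisted rescue is open during a pandemic. Section 7.9 limits rescue to its list without qualification, and the appendix states no exception.
- **Two rival definitions in section 10.3.7.** The test sentence drops the word permitted, but every definition and the synopsis keep it. This is probably shorthand. It still needs aligning, because the two wordings score these subjects in opposite ways.
- **Section 10.3.6 as proof that such subjects stay.** It bounds a hemoglobin window and names early termination as an alternative end, so it does not show that they are expected to remain.

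**Conclusion.** The point holds as a minor one. The definition in section 4.3, read with the closed list in section 7.9, gives the favourable score to a subject whose only AIHA rescue after Week 4 is non-permitted. Nothing in the supplied text corrects this. The number affected is unknown and probably small, and so is the direction: a reader might infer a bias towards fostamatinib, but the documents give no ground for placing these subjects in either arm. The harm is confined to endpoint 4 and, through the sequence, FACIT-F; the primary endpoint is not touched. One or two misplaced subjects matter only when the result is already near 0.05. The numerical illustration rests on assumed rescue rates, one stratum and hidden subjects placed in a single arm, except for the both-arms power figure. The conclusion about scoring needs none of these assumptions, but it would have to be revisited if the SAP, whose text was not supplied, already scores these subjects.

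**What to change.** 1. Define endpoint 4 as use of any AIHA rescue medication after Week 4, permitted or non-permitted, with non-permitted meaning what it already means in section 10.3.6. The exclusion-period rule needs the same classification and start date, so one derived flag serves both.
2. Use that wording in the synopsis, the objective in section 4.1, section 4.3, and both the summary and the CMH sentences of section 10.3.7.
3. Keep the permitted-only count as a descriptive summary.
4. Add a sensitivity analysis, consistent with the SAP's dropout rule, that scores withdrawal for need of non-allowed AIHA therapy or escalation as Yes. Keep this out of the main definition.
5. Appendix 7 needs at most a cross-reference to section 7.9.

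The cost is wording in the protocol and SAP, settled before unblinding. Sections 7.14 and 10.3.5 already provide for recording concomitant therapy, so no new data are needed. There are two downsides: the endpoint becomes slightly broader than it is now, and therapy started after a withdrawn subject's last follow-up visit may not be captured. Only the counting changes; no treatment, rescue or withdrawal rule does.

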#### 4.4 Safety Endpoints

The following safety endpoints will be evaluated:

- Incidence and severity of treatment-emergent adverse events (TEAEs)
- Incidence and severity of TEAEs of Interest
- Change from Baseline for select laboratory tests over time (e.g., hematology, chemistry)
- Change from Baseline in blood pressure over time
- Change from Baseline in absolute neutrophil count (ANC) over time
- Change from Baseline in liver function tests (i.e., alanine aminotransferase [ALT], aspartate aminotransferase [AST]), total bilirubin, direct and indirect bilirubin) over time.

#### 4.5 Additional Efficacy and Pharmacoeconomic Endpoints

The following additional efficacy and pharmacoeconomic endpoints will be evaluated:

- Any hemoglobin level  $\geq 10$  g/dL within the 24 weeks of treatment (Yes/No)
- Any change from Baseline in hemoglobin level  $\geq 1.5$  g/dL within the 24 weeks of treatment (Yes/No)
- Percentage of available visits with hemoglobin response
- Total duration of hemoglobin response (days)
- Total duration of hemoglobin  $\geq 10$  g/dL (days)
- Time to first hemoglobin response (days)
- Time to first rescue medication (days)
- Net cumulative change from Baseline in corticosteroid dose (prednisone-equivalent) during the 24 weeks of treatment
- Cumulative increase from Baseline in corticosteroid dose (prednisone-equivalent) during the 24 weeks of treatment.

- Change in reticulocyte count, LDH, and haptoglobin over time
- Change from Baseline to Week 24 in EQ-5D-5L
- Change from Baseline to Week 24 in the EQ VAS
- Hospitalization related to AIHA within 24 weeks of treatment (Yes/No).
- Change from Baseline in hemoglobin level over time during the 24 weeks of treatment

#### **4.6 Pharmacokinetic Endpoints**

The pharmacokinetic endpoint is the plasma concentration of the active component of fostamatinib (R406) relative to the date and time of last dose of study drug, at Weeks 2, 4, 12 and 18 of the treatment period.

## 5.0 STUDY DESIGN

[figure not shown]
### 5.1 Justification of Study Design

This is a Phase 3 multicenter placebo-controlled study to evaluate the safety and efficacy of fostamatinib in patients with wAIHA. The rationale for the study comes from results from a preclinical AIHA model showing that mice treated with fostamatinib were significantly protected from anemia (see [Section 3.2](#)) as well as results from a Phase II study showing that up to 47% of patients with wAIHA achieved a hemoglobin response after treatment with fostamatinib (see [Section 3.4](#)). The basis for a randomized controlled design is to be able to distinguish the safety and efficacy results of fostamatinib as compared to the control. The choice of a placebo for the control group is justified because there is no specific treatment approved for this condition. The initial hemoglobin response was observed in the Phase II study as early as week 2 and as late as week 30. The intent of the 24-week treatment and observation period is to capture the majority of responses.

